## 7 Analysis populations

The following analysis sets will be used in the statistical analyses.

### 7.1 Modified intention-to-treat population

All efficacy analyses will be conducted on the modified intention-to-treat (mITT) population which will comprise all randomized patients except patients who did not receive study treatment or patients who tested negative to SARS-Cov-2 diagnosis confirmation by PCR testing. In case of exclusion due to these criteria, additional patients may be recruited to ensure an adequate number of evaluable patients for the efficacy analysis.

Patients will be included in the group to which they were randomized for all efficacy evaluations.

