5.4.6 Blinding and unblinding

This is an open study with no level of blinding.

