5.5.1.3 Visit 1, Baseline (Day 1)

Once all inclusion and exclusion criteria have been reviewed and recorded, and the patient has been found eligible, the patient will be randomized into one of the treatment groups and the first dose of study drug will be administered accordingly (see Section 5.4.5). Please refer to Table 2 for other clinical and laboratory parameters to be collected during the visit.

During the treatment period (Days 1 to 15), clinical and laboratory assessments and procedures should preferably be performed before IMP administration.

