7.2 Definition of study populations

All efficacy analyses will be conducted on the modified intention-to-treat (mITT) population which will comprise all randomized patients except patients who did not receive study treatment or patients who tested negative to SARS-CoV-2 diagnosis confirmation by PCR testing.

In case of exclusion due to tested negative to SARS-CoV-2 diagnosis confirmation by PCR testing, additional patients may be recruited to ensure an adequate number of evaluable patients for the efficacy analysis.

The Safety population will comprise all patients who received at least one dose of study treatment or standard of care.

Patients will be included in the groups to which they were randomized for all evaluations of efficacy and in the groups according to treatment received for all evaluations of safety.

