## 4.3 Method of treatment assignment and randomization

This is a randomized, open-label study. The different treatment groups are;

Arm A: Emapalumab as add on to standard of care

Arm B: Anakinra as add on to standard of care

Arm C: Standard of care only

The sample size is 54 and the ratio between the treatment groups is 1:1:1, i.e., the same number of patients will be randomized to emapalumab, anakinra, or standard of care. Patients will be stratified based on glucocorticoid treatment at randomization to ensure an equal distribution between treatment arms. The randomization numbers are generated in blocks. Each block includes the three treatment groups per the ratio described above. An IWRS will be used for the randomization.

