### 7.2 Safety population

The Safety population will comprise all patients who received at least one dose of study treatment or standard of care.

Patients will be included according to treatment received for all evaluations of safety.

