## 8.2 Handling of missing data and outliers

### 8.2.1 Imputation of efficacy endpoints

For the primary endpoint (treatment success by Day 15), patients who discontinue study treatment (or discontinue the study if randomized to standard of care) prior to Day 15 and had IMV or ECMO on their last assessment by the time of study treatment discontinuation, will be considered not having achieved treatment success by Day 15. Patients discontinuing prior to Day 15 without ever having initiated IMV/ECMO, will be considered having achieved treatment success by Day 15. Patients discontinuing prior to Day 15 due to having significantly improved will be considered having achieved treatment success. Patients who died by Day 15, have not achieved treatment success regardless of IMV/ECMO use by Day 15.

For statistical analyses of change-from-baseline efficacy endpoints at Day 15, the last observation carried forward (LOCF) approach will be used to impute missing data, using the last post-baseline observation available for each patient.

For other efficacy presentations no imputation will be performed, i.e., all presentations will be based on observed data.

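### The mITT set drops never-treated patients from the two active arms only, with no all-randomised analysis behind it; the resulting bias can go either way

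*SAP*

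**What the plan says.** SAP 7.1 states that "All efficacy analyses will be conducted on the modified intention-to-treat (mITT) population" and defines that set as "all randomized patients except patients who did not receive study treatment or patients who tested negative" on PCR confirmation. Protocol 7.2 has the same rule: "all randomized patients except patients who did not receive study treatment", with the same PCR limb.

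The control group is "Arm C: Standard of care only" (SAP 4.3), and Protocol Table 1 lists no investigational product for it. Neither document says what receiving study treatment means for Arm C. Elsewhere the SAP keeps the two terms apart. The safety set (SAP 7.2) is "all patients who received at least one dose of study treatment or standard of care", and the missing-data rule (SAP 8.2.1) refers to "patients who discontinue study treatment (or discontinue the study if randomized to standard of care) prior to Day 15".

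Allocation is unmasked: "This is an open study with no level of blinding" (Protocol 5.4.6). Protocol 5.5.1.3 places randomisation and first dosing at one visit: "the patient will be randomized into one of the treatment groups and the first dose of study drug will be administered accordingly".

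The only sensitivity analysis named for the primary endpoint (SAP 12.1) is exact logistic regression on glucocorticoid stratum. No analysis of all randomised patients appears in either document.

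**The concern.** Read literally, the never-treated exclusion would empty Arm C. The only workable reading is that it acts on Arms A and B alone. The PCR-negative limb acts on all three arms and is not at issue.

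This makes it a post-randomisation, arm-specific exclusion applied with allocation known. An active-arm patient who dies or is intubated before the first infusion disappears, while the same patient in Arm C stays in as a failure. An active-arm patient who declines and leaves before dosing, without IMV or ECMO, also disappears, while the same patient in Arm C stays in as a success under SAP 8.2.1. Analysing patients in the group to which they were randomised does not help, because the patients concerned have already been removed.

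At stake is whether the primary test is still a randomised comparison. With 18 per arm, one patient is enough to matter. SAP 6 and Protocol 7.1 also allow a Stage 2 result significant at 5% to be treated as confirmed and used to seek approval.

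**Working it through.** **Inputs.** 18 per arm, 9 per arm at Stage 1; success rates 50% (SoC) and 80% (active); one-sided Fisher test; Stage 1 bounds p<0.025 (efficacy) and p>0.690 (binding futility); Stage 2 bound p<0.159 (SAP 5.1, 6 and 12.1; Protocol 7.1 and 7.3.6). The documents give no figure for how many patients will go untreated, or why, so those values below are assumptions.

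**1. Reproduce the plan's figures.** Exact enumeration of the two-stage design at 80% vs 50% gives power 0.736, against 74% stated. SAP Table 1 lists 14 vs 10 and 15 vs 11 as Stage 2 efficacy boundaries; the p-values here agree (0.145 and 0.132).

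**2. One exclusion at Stage 2.** With a/n1 successes on active and c/n2 on SoC, p = Σ(x≥a) C(n1,x)·C(n2,a+c−x) / C(n1+n2,a+c). For 14/18 vs 11/18 this is Σ(x=14..18) C(18,x)·C(18,25−x)/C(36,25) = 0.235. Removing one active failure gives Σ(x=14..17) C(17,x)·C(18,25−x)/C(35,25) = 0.155.

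| All randomised | p | After one active exclusion | p | Decision at 0.159 |
|---|---|---|---|---|
| 14/18 vs 11/18 | 0.235 | failure dropped: 14/17 vs 11/18 | 0.155 | not met → met |
| 15/18 vs 12/18 | 0.222 | failure dropped: 15/17 vs 12/18 | 0.132 | not met → met |
| 14/18 vs 10/18 | 0.145 | success dropped: 13/17 vs 10/18 | 0.172 | met → not met |
| 13/18 vs 9/18 | 0.153 | success dropped: 12/17 vs 9/18 | 0.185 | met → not met |

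**3. Bias in the active success rate.** Let P be the true rate in the whole arm, u the untreated fraction and s the success rate among the untreated. The rate among those kept is (P − u·s)/(1 − u). With P=0.50:
- u=1/18: s=0 gives 0.500/0.944=0.529 (+2.9 points); s=0.5 gives no bias; s=1 gives 0.471 (−2.9 points).
- u=2/18: s=0 gives 0.5625 (+6.3 points); s=1 gives 0.4375 (−6.3 points).

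**4. Final-look false-positive rate.** The true rate is 50% in both arms. The number treated in the active arm is Bin(18, 1−u), with success rate from step 3; control is Bin(18, 0.5); rejection is at p<0.159.

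| Success among untreated | u=10% | u=5% |
|---|---|---|
| 0% | 16.4% | 13.3% |
| 20% | 13.3% | 12.0% |
| 30% | 12.0% | 11.4% |
| 50% | 9.6% | 10.3% |
| 80% | 6.6% | 8.7% |
| *No exclusion* | *12.1%* | *12.1%* |

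The fall at 50% success is not bias. It comes from the discreteness of Fisher's test with unequal arms: with 17 or 16 active patients removed at random the rate is 8.8% or 9.4%, against 12.1% with 18.

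**5. Both stages together.** With the Stage 1 rules included, the rate at 50%/50% is 11.7% with no exclusion. As a bound, suppose the dropped active patient is always a failure whenever one exists: one dropped gives 11.9–12.5%, two (one per stage) 17.7%. If always a success: 6.4–6.9%, and 4.9%. Power moves from 0.736 to 0.77–0.80 and 0.86 in the first case, and to 0.66 and 0.63 in the second.

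The 11.7% exceeds the 9.7% that the plan states. That is a separate matter; here it serves only as the reference.

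**The case against.** A reader might infer that the rule necessarily favours the active drugs and inflates the false-positive rate. The documents do not support this. They do not say why patients would go untreated, and the outcome rules point both ways: death or ongoing IMV/ECMO counts as failure, but leaving without ever starting either counts as success. With 10% untreated, the final-look rate is back at its reference once about 30% of the untreated would have succeeded; with 5% untreated, at about 20%. An inflation figure quoted alone would rest on an unsupported untreated rate and on near-certain failure among those patients.

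Opportunity is also limited. Randomisation and first dosing share a visit, and exclusion criterion 1 (Protocol 5.3.2) is aimed at patients already ventilated or worsening rapidly. This stands as a reason to expect few cases. It does not rule them out, and Protocol 5.4.7.1, which requires zoster prophylaxis from the day before the first emapalumab dose, does not sit easily with same-visit dosing; the two passages should be reconciled.

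The asymmetry is inferred from usage, because study treatment is never defined for Arm C. That is fair, but the alternative literal reading leaves no control arm.

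Finally, Protocol 3.1 calls the study proof of concept, with a type I error chosen to detect a signal. That softens the point only in part, given the route to regulatory use at 5%.

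**Conclusion.** The point holds as one of asymmetry with unknown direction. The never-treated limb can act only on the active arms, after open allocation, and it applies to every efficacy analysis with no all-randomised analysis as a check. It can bias the primary comparison towards active or against it.

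The expected number of such patients is small, but a single one can reverse a Stage 2 decision in either direction. Assuming a 50% null rate and 0–80% success among the untreated, the final-look false-positive rate runs from 16.4% to 6.6% with 10% untreated and from 13.3% to 8.7% with 5%, against 12.1% with no exclusion. Neither the untreated rates nor the success rates among the untreated come from the documents. A claim that the bias favours active would need evidence on who goes untreated, and the plan has none. This is an inexpensive improvement, not a finding that the result will be wrong.

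**What to change.** - In SAP 7.1 and Protocol 7.2, make the primary efficacy set all randomised patients, excluding at most PCR-negative patients by the same rule in all three arms.
- Keep untreated patients in their randomised arm at their observed Day 15 IMV/ECMO/death status. Where that status is not observed, state that SAP 8.2.1 applies identically in every arm.
- Retain the current mITT set as a sensitivity analysis, and say in it what receiving study treatment means for Arm C.
- Reconcile the recruitment provisions: SAP 7.1 allows additional patients for both exclusion reasons, Protocol 7.2 only for PCR-negative patients.

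The cost is wording in two documents. Keeping untreated patients retains the planned 18 per arm, on which the 74% power rests. The downside is a slight dilution of the effect if a few patients are never treated.

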### 7.2 Safety population

The Safety population will comprise all patients who received at least one dose of study treatment or standard of care.

Patients will be included according to treatment received for all evaluations of safety.

## 8 General issues for statistical analysis

Results will be presented as the estimated value for each treatment group, emapalumab, anakinra and standard of care, the estimated difference between emapalumab/anakinra and standard of care, the associated confidence interval and p-value. P-values from statistical analyses will be presented to three decimal places with values below 0.001 displayed as <0.001 and confidence intervals will be presented to one more decimal place than the raw data.

Continuous data will be summarized using descriptive statistics: n, mean, SD, median, minimum and maximum, unless otherwise indicated. Minimum and maximum will be presented to the same number of decimal places as the raw data and mean, SD, and median will be presented to one more decimal place than the raw data.

Categorical data will be summarized using counts and percentages. Percentages will be suppressed when the count is zero, however the category will still be displayed. The denominator for all percentages will be the number of patients within the treatment group for the population of interest, unless otherwise indicated. Percentages will be presented to one decimal place.

All efficacy endpoints will be analyzed and summarized for the mITT population and safety data will be presented for the safety population.

Statistical analyses will be performed using SAS software Version 9.4 (SAS Institute Inc, Cary, North Carolina, United States).

## 8.1 Time windows

For the purpose of the statistical analysis and if not otherwise specified, all the variables (primary, secondary and exploratory variables) will be assigned to the visit/assessment timepoint in which they were collected depending on the following analysis time windows in Table 1.

**Table 2 Time windows**

Visit	Study Day	Study Day window
1	1 (Baseline)	≤1
2	4	2-5
3	7	6-8
4	10	9-11
5	13	12-14
6	15	15-16
7	28	Early follow-up
7/TC	Week 6	Only follow-up of survival and hospital discharge and continued AE reporting in accordance with the protocol.
8/TC	Week 10	

Unscheduled visit data will be considered when assigning assessments to the analysis visit. If more than one assessment of the variable (scheduled or unscheduled) falls in the same time window but on different days, the closest to the scheduled visit day will be taken, or the earlier, in the event the values are equidistant from the nominal visit date. If several measurements are collected during the selected day, the average (for numeric values)/worst (for categorical values) of the measurements will be taken.

In summaries of extreme values as opposed to visit-based summaries, all post baseline values collected are used including those collected at unscheduled visits regardless if the value is closest to the scheduled visit date or not. For summaries at a patient level, all values should be included, regardless of whether they appear in a corresponding visit-based summary, when deriving a patient level statistic such as a maximum.

Listings will display all values contributing to a time point for a patient.

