5.5.1.4 Visits 2 to 5 (Days 4, 7, 10 and 13)

Please refer to Table 2 for the clinical and laboratory parameters to be collected during these visits. For study drug administration schedule, see Section 5.4.5.

Effort should be made to adhere to the schedule of assessment. However, a window of ± 1 day will be allowed for all assessments scheduled for Visits 2 to 5. This does not include IMP administration.

During the treatment period (Days 1 to 15), clinical and laboratory assessments and procedures should preferably be performed before IMP administration.

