5.5.1.5 Visit 6 (Day 15)

Please refer to Table 2 for the clinical and laboratory parameters to be collected during these visits. For study drug administration schedule, see Section5.4.5.

Effort should be made to adhere to the schedule of assessment. However, a visit window of ± 1 day will be allowed for Visit 6 (Day 15).

During the treatment period (Days 1 to 15), clinical and laboratory assessments and procedures should preferably be performed before IMP administration

The primary endpoint will be evaluated at Visit 6 (Day 15).

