### **12.2.6 Amelioration of the findings of high-resolution CT scan or X-ray of the chest**

Amelioration in the findings of high-resolution CT scan or X-ray of the chest will be summarized in a shift table showing the number and percentage of patients that had normal, abnormal (not clinically significant) or abnormal (clinically significant) findings at screening and at Day 15.

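### SAP Table 2 gives Day 14 to Visit 5, so a protocol-compliant Visit 6 held on Day 14 is missing from the observed-data Day 15 displays

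*SAP*

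**What the plan says.** On visit timing, Protocol 5.5.1.5 states that "a visit window of ± 1 day will be allowed for Visit 6 (Day 15", which makes Days 14, 15 and 16 all valid for Visit 6; the Schedule of Events agrees. Protocol 5.5.1.4 says ± "1 day will be allowed for all assessments scheduled for Visits 2 to 5", so Visit 5 (nominal Day 13) may fall on Days 12 to 14. The two visits share Day 14.

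SAP 8.1 applies its own windows broadly: unless otherwise specified, "all the variables (primary, secondary and exploratory variables) will be assigned to the visit/assessment timepoint" according to study day. SAP Table 2 gives Visit 5 Days 12-14 and Visit 6 Days 15-16. When a window holds values from several dates, the rule is that "the closest to the scheduled visit day will be taken". A tie goes to the first of them.

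SAP 8.2.1 fills missing Day 15 values in the change-from-baseline statistical analyses by LOCF, "using the last post-baseline observation available for each patient". Other efficacy presentations use observed data only. One of these is the imaging shift table in SAP 12.2.6, which reports "findings at screening and at Day 15".

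**The concern.** A site can follow the protocol exactly, hold the end-of-treatment visit on Day 14, and have the analysis dataset record no Visit 6. The Day 14 record goes to Visit 5, where it competes with the real Visit 5 record and usually loses. The Day 15 column then shows a patient as missing who was seen, on time, for that visit.

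At stake are the Day 15 descriptive results: the by-visit summaries of laboratory values, SpO2, oxygen supplementation and hemogasanalysis, the CT/X-ray shift table, the 7-point scale, and possibly the summary of patients with at least 50% improvement in hyperinflammatory parameters. With 18 patients per arm, a few such losses would change these tables visibly.

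**Working it through.** The plan states no figure to reproduce. The check sets the windows side by side and then applies the SAP rule to every permitted combination of visit days.

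**Step 1: protocol window against SAP window** (Protocol 5.5.1.4 and 5.5.1.5; SAP Table 2)

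| Visit | Nominal day | Protocol days | SAP days | Protocol days outside the SAP window |
|---|---|---|---|---|
| 2 | 4 | 3-5 | 2-5 | none |
| 3 | 7 | 6-8 | 6-8 | none |
| 4 | 10 | 9-11 | 9-11 | none |
| 5 | 13 | 12-14 | 12-14 | none |
| 6 | 15 | 14-16 | 15-16 | **14** |

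Day 14 for Visit 6 is the only mismatch in Visits 2 to 6.

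**Step 2: what happens to a Visit 6 held on Day 14.** Distance is the absolute difference between the actual day and Day 13, because the record is now in the Visit 5 window. The Day 14 record has distance |14 − 13| = 1.

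| Visit 5 held on | Its distance | Value kept for Visit 5 | Day 14 value | Scheduled value in Visit 6 window |
|---|---|---|---|---|
| Day 13 | 0 | Day 13 (closer) | unused | none |
| Day 12 | 1 | Day 12 (tie, earlier wins) | unused | none |
| Day 14 | 1 | Day 14 | used as Visit 5 | none |
| missed | – | Day 14 | used as Visit 5 | none |

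A Visit 6 on Day 15 or 16 is kept as Visit 6 in every case. Only an unscheduled record on Day 15 or 16 could fill the empty cell.

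**Step 3: which variables are dropped and which only relabelled** (Protocol Table 2)

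- Measured at Visits 5 and 6 (laboratory values, SpO2, hemogasanalysis, oxygen supplementation, 7-point scale): rows 1 and 2 apply, and the Day 14 value is lost to the earlier one.
- Not scheduled at Visit 5 (imaging, MEWS, PaO2/FiO2): nothing scheduled competes, so the Day 14 value survives under the Visit 5 label.

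**Step 4: consequence by type of analysis**

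- Observed-data Day 15 displays: the patient is missing for both groups of variables.
- Day 15/LOCF ANCOVAs: the patient stays in. If LOCF draws on all records, the Day 14 value comes back. If it draws only on window-selected values, a Day 13 or Day 12 value replaces it for the first group of variables. The SAP does not say which. For MEWS and PaO2/FiO2 the Day 14 value is used on either reading.
- Primary endpoint: a patient who never starts IMV/ECMO is a success, and one who dies by Day 15 is a failure, whatever the window. Under SAP 8.5.1, status at Day 15 matters for a patient ventilated earlier. Protocol 5.5.3.1 records the date and time of the IMV/ECMO requirement, which may settle such cases. No rule covers a continuing patient for whom those dates do not settle it and who has no record on Days 15-16.

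**Step 5: size.** The documents do not say how often Visit 6 would fall on Day 14. The range is 0 to 18 per arm; each patient is 1/18 = 5.6% of an arm.

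**The case against.** The best case on the other side is that the harm is narrow, and most of that case stands.

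- LOCF, read plainly, takes the last available observation, which is the Day 14 value. On that reading the ANCOVA results do not change and only the label is wrong. The SAP does not confirm this reading, so the exposure is conditional.
- The improvement and normalisation summaries may escape. Normalisation is judged by Day 15, which a Day 14 value can satisfy, and SAP 8.1 lets patient-level summaries use every collected value. It is not clear that this sentence covers the 50% improvement summary.
- Protocol 7.3.1 treats the secondary endpoints as descriptive, with any p-values exploratory. The 7-point scale is itself an exploratory endpoint.

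A reader might infer that a third of patients are affected, since one of the three permitted days is misassigned. That assumes visits spread evenly over Days 14 to 16. Protocol 5.5.1.5 instead asks sites to try to keep to the schedule, so the documents give no basis for that figure.

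A reader might also infer that the primary result is at risk. At the Stage 2 size, 13 against 9 successes of 18 gives a one-sided Fisher p of 0.153, below the 0.159 threshold, while 12 against 9 gives 0.250, so one changed status can matter. That shows how sensitive the test is. It does not show that this window changes anyone's status: SAP 8.5.1 has its own derivation, the windows apply only where nothing else is specified, and IMV/ECMO dates are recorded.

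What the objection does not remove is the conflict itself, or the empty Day 15 cell in observed-data displays.

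**Conclusion.** The two documents disagree about Day 14. Following the SAP as written leaves a compliant Day 14 Visit 6 without a scheduled value in every observed-data Day 15 display. The value is discarded for variables also measured at Visit 5 when a Day 13 or Day 12 value exists, and relabelled for imaging, MEWS and PaO2/FiO2. The ANCOVAs lose the Day 14 value only if LOCF is limited to window-selected data. The primary endpoint is touched, if at all, only for patients ventilated earlier whose Day 15 status the recorded dates leave open.

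The number of patients affected is unknown and may be zero. The conclusion assumes that the windows are programmed literally and that no unscheduled record falls on Day 15 or 16. This is an alignment error that should be corrected; it does not undermine the trial's main comparison.

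**What to change.** In SAP 8.1, assign a scheduled assessment to its nominal CRF visit when it falls inside that visit's protocol window (Visit 5: Days 12-14; Visit 6: Days 14-16). Use the day windows only for unscheduled or out-of-window records. Give scheduled records precedence over unscheduled ones in the same window. A Day 14 Visit 6 then counts as the Day 15 value, so LOCF is not needed for it.

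Moving the Table 2 boundary alone (Visit 5 to Days 12-13, Visit 6 to Days 14-16) is not enough, because the protocol windows overlap on Day 14. A late Visit 5 or an unscheduled record on Day 14 would then tie with a genuine Day 16 Visit 6 (|14 − 15| = |16 − 15| = 1) and win as the earlier value. That would discard a value the current table keeps.

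The cost is a short SAP edit and a small programming change to the visit-assignment rule. No extra data are needed.
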